3 INVESTIGATIONAL PLAN

3.1 Overview of Study Design

The purpose of this randomized blinded study is to evaluate whether oseltamivir modifies viral shedding in an ambulatory population with uncomplicated influenza. This study is also designed to explore the relationship between virologic effects and clinical effects, effects on pro-inflammatory mediators, and to start understanding if improvements to virologic shedding correlate with improvements in clinical outcomes. For this reason, the study is powered to show an anticipated difference in virologic shedding. This is a multicenter international study. Up to approximately 50 sites may participate in this protocol.

It is anticipated that about 800 subjects may be enrolled to allow 560 eligible subjects to be randomized in this study. The anticipated study duration is 7 years. The original sample size of the study was powered to show a difference in virologic shedding as detected by TCID₅₀ (as detailed in Section 9.2). With new virologic techniques such as PCR, it is anticipated that the objectives of this study may be achievable with smaller numbers of subjects; therefore the sample size has been reduced.

Subjects with an influenza-like illness will be screened for the study, and those found positive for influenza will be randomized in a 1:1 manner to receive a blinded study treatment consisting of either oseltamivir or placebo for 5 days. The study arms are as follows (Table 2):

Table 2: Treatment Allocation

| Arm | Drug | Allocation Ratio | Capsule |
|-----|---------------------|------------------|-------------|
| 1 | Oseltamivir | 1 | Oseltamivir |
| 2 | Oseltamivir placebo | 1 | Placebo |

Subjects will be assessed on Study Day 0 (pre-dose), and on Study Days 3, 7, and 28. All subjects will undergo a series of efficacy and safety assessments during the study. Blood samples will be collected on Days 0, 3, 7, and 28.

Table 4 in Section 6 presents the schedule of assessments. A detailed presentation of assessments to be conducted at each visit is presented in Section 6.3.

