3.3.2 Secondary Endpoints

Clinical Endpoints:

- Time to alleviation of influenza clinical symptoms
- Time to absence of fever
- Time to resumption of normal activity
- Number of premature study treatment discontinuations
- Proportion of subjects who develop bronchitis, pneumonia, or other complications of influenza
- Proportion of subjects who require hospitalization
- 28-day mortality

Virologic Endpoints: (assessed by PCR in NP swab)

- Duration of viral shedding
- Change in viral shedding as a function of time
- AUC of viral shedding
- Frequency of emergence of antiviral resistance

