9.1 General Considerations

All statistical inferences will be based on two-sided tests with an α -level of 0.05. Categorical data will be summarized by the number and percent of subjects falling within each category. Continuous variables will be summarized by descriptive statistics, including mean, standard deviation, minimum, maximum, median, and relevant percentiles. Time-to-event endpoints will be summarized by median durations, hazard ratios, and corresponding 95% confidence intervals. Study Day 0 will be defined as the day of randomization.

The Statistical Analysis Plan will provide the procedure for accounting for missing, unused, and spurious data.

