9.2.1 Sample Size Re-estimation

After analysis of the pilot study data, the primary endpoint was chosen as the percentage of subjects shedding virus by PCR in NP swab at Day 3.

Assumptions:

- Pooled percentage of subjects with virus detectable by PCR at Day 3 combining both arms is 50% (based on pilot study data)
- Require 90% power to detect difference between arms using two-sided Fisher’s Exact Test with Type I error rate of 0.05.
- Proportion of participants with missing qPCR at Day 3 is 10% (due to losses to follow-up, sample handling and laboratory assay problems).

| Magnitude of difference in proportions between arms (proportions in the two randomized arms) | Sample size (combined across both arms) without adjustment for missing values | Sample size (combined across both arms) with adjustment for 10% with missing values & not accounting for the 50 subjects in the pilot study) |
|--|---|--|
| 25% (37.5% vs 62.5%) | 174 | 194 |
| 20% (40% vs 60%) | 280 | 312 |
| 15% (42.5% vs 57.5%) | 490 | 546 |

Table 9: Re-estimated Sample Size Under Different Treatment Effects

This sample size has been chosen to give approximately 90% power to detect an absolute difference of 15% in the proportion of subjects with undetectable virus shedding at Day 3 in NP swabs (e.g., a reduction of 15% from 57.5% in the oseltamivir arm to 42.5% in the placebo

arm). Less than a 15% absolute difference in viral shedding is unlikely to be viewed as clinically meaningful. Therefore, the revised sample size calculations confirm keeping the sample size 560 subjects, including 50 in the pilot study and 510 in the main study.

This power calculation is based on the fact that approximately 50% of subjects in the pilot study had undetectable virus in NP swabs at Day 3 (pooled over randomized arms) and included allowance for 10% of subjects to have unavailable viral shedding results at Day 3. The calculation assumed use of a t-test to compare proportions using a two-sided type I error rate of 0.05.

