#### 4.8 Efficacy Analysis

The following efficacy analyses will be presented for the Primary Efficacy Population (study participants with confirmed influenza) and also for the Intent to Treat Population. The primary analysis of the primary endpoint will exclude the 50 subjects enrolled in the pilot study. A secondary analysis will, however, be undertaken which includes these 50 subjects. All analyses of secondary efficacy endpoints will be undertaken including the 50 subjects enrolled in the pilot study.

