#### **4.9 Secondary Endpoints: Clinical Endpoints [DIARY1] (PEP and ITT)**

Many of the clinical endpoints rely on data collected on diary cards completed by the study participants. The subjects are asked to complete these twice a day (at 8AM and 8PM) on Days 0 through 14 and then again on Day 28. Fever is recorded for the preceding 12 hour period at both times each day, and symptoms are recorded at both times for Days 0 to 7 and then once daily on Days 8 to 14. Functional status (based on the Physical Function domain questions from the SF-36) and two questions giving a global assessment of status are completed daily at 8AM.

- a. Duration of clinical symptoms. Duration of clinical symptoms is defined as the time from Day 0 to the first of two successive measurements at which all clinical symptoms are grade 0 (absent) or 1 (mild). A measurement is considered to be the 8AM or 8PM assessment during Days 0 to 7 (so two measurements are obtained per day) and then the daily assessment thereafter. Time will then be calculated in half-days through to Day 7. For the purposes of defining the endpoint, if the subjects' first two assessments on (baseline assessment and first subsequent diary card assessment) satisfy this criterion, then the duration will be set to zero. Missing values will be ignored [this is equivalent to assuming that a missing value would have (a) indicated at least one grade 2+ symptom if the preceding record includes a grade 2+ symptom or if the first Day 0 value is missing; (b) indicated no grade 2+ symptoms if the preceding and succeeding assessments show no grade 2+ symptoms; and (c) indicated a grade 2+ symptom if the preceding assessment shows no grade 2+ symptom and the succeeding value shows a grade 2+ symptom]. Times will be considered as discrete (i.e. based on the schedule of completion of diary cards) and subjects not having two succeeding assessments with only grade 0 or 1 symptoms at any time during follow-up will be censored immediately after Day 14 (the last scheduled measurement time on which an endpoint can occur).
- Kaplan-Meier plot (and associated table) of the percent of subjects without clinical symptoms per the above definition over time, with the median duration of time to alleviation of such symptoms and its 95% confidence interval.
  - P-value comparing randomized arms from the log rank test.

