  - Kaplan-Meier plot (and associated table) of the percent of subjects returning to pre-illness level per the above definition over time, with the median duration of time to return and its 95% confidence interval.
  - P-value comparing randomized arms from the log rank test.
- f. The following outcomes are targeted in the protocol:
- Bronchitis / bronchiolitis
  - Pneumonia
  - Other complications

For each of these, the percentage of subjects experiencing the event during follow-up will be obtained with the associated 95% confidence interval and comparison of arms will be based on the normal approximation to the binomial distribution, or exact methods based on the binomial distribution if numbers are small.

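### SAP 4.9f analyses bronchitis, pneumonia and other complications one by one, so the single complications proportion listed as a secondary endpoint gets no result

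*SAP*

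**What the plan says.** Protocol 3.3.2 lists among the clinical secondary endpoints the "Proportion of subjects who develop bronchitis, pneumonia, or other complications of influenza". The same single line stands in the protocol summary, among the secondary objectives (Protocol 2.2), and in the SAP's own lists of objectives and endpoints.

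SAP 4.9 item f turns this into three outcomes: bronchitis/bronchiolitis, pneumonia, and other complications. It continues: "For each of these, the percentage of subjects experiencing the event during follow-up will be obtained with the associated 95% confidence interval". Each outcome also gets its own between-arm test, by a normal approximation or, where counts are low, by an exact binomial method. The section is headed "Secondary Endpoints: Clinical Endpoints [DIARY1] (PEP and ITT"), so each comparison is made in two populations.

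On error control, Protocol 9.1 says "All statistical inferences will be based on two-sided tests with an α -level of 0.05". Neither document states a multiplicity adjustment for any secondary endpoint.

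No other SAP section fills the gap. Section 4.6 covers death and hospitalization, and 4.3.3 item n only describes complications present at Day 0.

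**The concern.** The ordinary meaning of the endpoint line is the share of subjects with at least one complication. The SAP plans three other quantities and never this one. Followed exactly, the plan leaves a listed endpoint without an estimate, interval or test.

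Two features of the SAP suggest an oversight. When it splits another endpoint, resumption of normal activity, into several measures, it says so in an explicit note in both lists; complications have no such note. For serious adverse events, 4.7.1 gives the breakdown and also the number of subjects with any event; 4.9f has no such total.

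What is at stake is the trial's statement on whether oseltamivir reduces complications. If the three components point in different directions, the choice of which to present as the endpoint result could be made after the data are seen.

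**Working it through.** **Inputs.** The total is 560, "including 50 in the pilot study and 510 in the main study" (Protocol 9.2.1). Subjects "those found positive for influenza will be randomized in a 1:1 manner" (Protocol 3.1). SAP 4.8 adds: "All analyses of secondary efficacy endpoints will be undertaken including the 50 subjects enrolled in the pilot study". That gives 560 / 2 = 280 per arm, a ceiling, since the ITT population requires at least one dose and the PEP requires central confirmation. (Protocol 9.5 would exclude the pilot subjects from secondary efficacy analyses: 510 / 2 = 255 per arm.) Tests are two-sided at 0.05. Neither document gives a complication rate, effect size or power for this endpoint, so all rates below are assumptions.

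**Check of the tool.** There is no plan figure for this endpoint to reproduce. For the primary endpoint, the same exact Fisher enumeration at 245 per arm, 42.5% against 57.5%, gives 90.3% power, in line with the 490 at 90% in Protocol 9.2.1.

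**Step 1: can the listed proportion be recovered?** With component proportions b, p and o, the proportion with at least one lies between max(b, p, o) and b + p + o, according to overlap. Take assumed placebo rates of 5%, 2% and 8%, each halved on oseltamivir.
- Placebo: between 8% and 5 + 2 + 8 = 15%.
- Oseltamivir: between 4% and 2.5 + 1 + 4 = 7.5%.
- Difference: between 8 − 7.5 = 0.5 and 15 − 4 = 11 percentage points.

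The same three reported percentages per arm are compatible with a combined difference anywhere from 0.5 to 11 points. The planned output does not determine it.

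**Step 2: false-positive chance if any significant component is taken as the answer.** For three independent tests at 0.05 the nominal figure is 1 − (1 − 0.05)³ = 0.1426, and at most 3 × 0.05 = 0.15 whatever the dependence. The actual figure depends on the test and the rates. Exact enumeration at 280 per arm, with independent components, gives:

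| Assumed rates: bronchitis, pneumonia, other | Any of three, normal approximation | Any of three, Fisher |
|---|---|---|
| 1%, 0.5%, 2% | 11.65% | 3.41% |
| 2%, 1%, 4% | 13.71% | 6.27% |
| 3%, 1%, 5% | 13.95% | 6.86% |
| 5%, 2%, 8% | 14.10% | 8.58% |
| 10%, 5%, 10% | 14.21% | 10.16% |

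One test of the combined proportion has 4.99% to 5.09% (normal approximation) or 2.97% to 3.93% (Fisher) across these rows. Fisher's test stands in for the exact methods that 4.9f prescribes for small numbers without naming one.

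**Step 3: power, same rates as placebo rates, normal approximation.**

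| Placebo rates | All risks halved: combined / any of three / best single | Bronchitis only, risk ratio 0.2: combined / bronchitis test |
|---|---|---|
| 1%, 0.5%, 2% | 25.0% / 24.4% / 14.8% | 8.3% / 18.4% |
| 2%, 1%, 4% | 44.6% / 44.4% / 28.5% | 11.7% / 41.3% |
| 3%, 1%, 5% | 55.1% / 53.4% / 34.4% | 17.2% / 59.2% |
| 5%, 2%, 8% | 76.9% / 73.2% / 52.2% | 25.0% / 83.9% |
| 10%, 5%, 10% | 93.5% / 90.7% / 62.4% | 53.3% / 98.9% |

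With a shared effect, the combined test beats any single component but gains only 0.2 to 3.7 points on the any-of-three rule (6 to 10 points with Fisher). With an effect confined to bronchitis the order reverses in all five rows, and in four of five with Fisher.

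**The case against.** The endpoint line can be read as a list. Neither document calls it a composite, and 4.9f introduces its three items as outcomes that the protocol targets. This is possible but less natural: a proportion of subjects who develop one thing, another, or others ordinarily counts each subject once. The SAP also repeats the line unchanged, without the note it uses elsewhere when it splits an endpoint.

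A reader might infer that three tests in place of one mean a 14% error rate and a loss of power. The documents support neither as a flat statement. The 14% belongs to the normal approximation; if events are rare, 4.9f moves to exact methods, and the figure can fall to about 3%. Positive correlation between components would lower it further. The power comparison turns on rates and an effect pattern that the documents do not give. The other category may also include antibiotic use for another reason (Protocol 7.3.2), which could dilute a combined effect.

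It is also fair that this is one of many secondary endpoints, that none has multiplicity control, and that the trial is powered for viral shedding. No confirmatory error rate is breached. Repeating the tests in the PEP and ITT adds little, because the populations overlap heavily. These points limit the consequences. They do not supply the missing analysis.

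**Conclusion.** The point holds as a mismatch between a listed endpoint and its analysis. This rests on the wording alone and needs no assumed rates: one proportion is listed, three others are analysed, and the listed one cannot be derived from them. With no rule for choosing among the three, reading any significant component as the endpoint result has a false-positive chance of roughly 3% to 14%. That range assumes 280 per arm, independent components and the rates tabulated above. The combined test may have more or less power than the component tests, so no general power loss is asserted. The matter is secondary but should be settled before unblinding.

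**What to change.** In SAP 4.9 item f, state that the listed complications endpoint is analysed as the proportion of subjects with at least one of bronchitis/bronchiolitis, pneumonia or other complications during follow-up. Report the between-arm difference, 95% confidence interval and p-value by the method 4.9f already gives. Keep the three component analyses, labelled supportive; their p-values need not be removed. The combined variable should use the same content for other complications as the component analysis.

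The cost is one derived variable from data already collected (Protocol 7.3.2 and the schedule of assessments) and one extra table row for each population. The small downside is that a combined proportion can dilute an effect confined to one component; that effect stays visible in the component results.

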#### **4.9.1 Association of viral shedding to clinical symptoms and fever (PEP and ITT)**

Association between viral shedding and clinical symptoms and fever is listed as a secondary objective. The analysis depends on what is seen in virology results, and therefore the analysis is not presented in this analysis plan. The planned analysis will be detailed in a later analysis plan.

#### **4.10 Evaluation of self-collected samples (PEP and ITT)**

Self-collected NP are collected on Day 0 (prior to treatment initiation), Day 0 evening, Day 1, Day 1 evening, Day 2, Day 2 evening and Day 3. Viral shedding will be assessed using these self-collected swabs by the same assay used for the team collected swabs, i.e., quantitative RT-PCR (reported as  $\log_{10}$  RNA copies/mL).

- a. Completeness of viral shedding results showing number (%) at Day 0, Day 0 evening, Day 1, Day 1 evening, Day 2, Day 2 evening and Day 3 who:
  - had swab taken (i.e. submitted)
  - had qPCR result
  - died prior to visit
  - were lost to follow-up prior to the visit
  - were in follow-up but had missing value
- b. Among subjects with Day 3 qPCR results, number (%) with detectable viral shedding at Day 3. Comparison of randomized arms with associated 95% confidence interval and p-value based on the normal approximation to the binomial distribution. This table can be compared to table 4.8.1a, the primary endpoint, to determine if the self-swabs would have similar treatment effects
  - Repeat analysis in the population for the primary analysis (PEP excluding pilot study) to allow direct comparison with primary endpoint.
- c. Bland-Altman plot showing the agreement between the result from the self-collected swabs and team-collected swabs across all available swabs
- d. Bland-Altman plot showing the agreement between the result from the self-collected swabs and team-collected swabs on Day 0 and Day 3.
- e. Table: Mean, standard deviation, median, min, max, 25% and 75% percentiles of the viral load difference between self-collected swabs and team-collected swabs on Day 0, Day 1, Day 2 and Day 3. P-values comparing the difference based on normal approximation or Wilcoxon signed rank test, as appropriate for the data.
- f. Plots of associations between viral load based on self-collected swabs and viral load based on team-collected swabs on Day 0, Day 1, Day 2 and Day 3. Spearman correlation coefficients, along with their 95% confidence intervals, will be provided. Plots of associations and estimated correlation coefficients will be provided both over all subjects and by strata defined by quartile of the viral load based on team-collected swabs at each time point.
- g. AUCs will be calculated for the self-collected swabs. This is defined as the area below the line formed by joining the measured values at each successive scheduled measurement time and above the limit of detection. This will be calculated using the trapezoidal rule. Missing values will be ignored (this is equivalent to imputing a missing value using linear interpolation between the previous and succeeding available values). If the Day 0 value is missing, then the subject will be excluded from the analysis.
  - Figure and associated table showing number of subjects and minimum, maximum, median, 25% and 75% percentile of the value of viral shedding at each scheduled measurement time. This will be presented (a) imputing values

as defined above for the calculation of AUC, and (b) using observed values only.

- Table showing number of subjects and minimum, maximum, median, 25% and 75% percentile of the AUC, both over all subjects and by strata defined by quartile of Day 0 measurement.
- P-value comparing randomized arms from Wilcoxon rank sum test stratified by quartile of Day 0 measurement.

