##### 4.8.1 Primary Endpoint [IRCRSLT] (population for the primary analysis and PEP)

The primary endpoint is defined as the percentage of subjects shedding virus by PCR in nasopharyngeal swabs obtained at Day 3.

- a. Completeness of viral shedding results showing number (%) at Day 0, 3 and 7 who:
  - had qPCR result
  - were lost to follow-up prior to the visit
  - were in follow-up but had missing value
- b. Primary Analysis: Among subjects with Day 3 qPCR results, number (%) with detectable viral shedding at Day 3. Comparison of randomized arms with associated 95% confidence interval and p-value based on the normal approximation to the binomial distribution.

- c. Sensitivity Analyses (PEP only): to assess potential impact of missing measurements. Repeat the primary analysis (above) considering missing measurements in turn as (a) above the limit of detection, or (b) below the limit of detection, or (c) above the limit of detection in one randomized arm and below in the other arm (so as to maximize the difference between arms), or (d) the opposite of (c) (so as to minimize the difference between arms).
- d. Sensitivity Analyses (PEP only): Repeat the primary analysis above but restricted (a) to samples in which one or more housekeeping genes had detectable levels (hence indicating adequate sample); and (b) to samples in which all housekeeping genes had detectable levels.
- e. Subgroup Analyses (PEP only): Comparison of randomized treatments will be undertaken by sex (male vs female), influenza type (A vs B), and country/race (US/white vs US/non-white vs Thailand vs other countries). To assess whether the difference between randomized treatments varies by subgroup, a treatment by subgroup interaction test will be undertaken using logistic regression.

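### SAP 4.10b sets out to determine whether self-swabs show a similar treatment effect, but plans no estimate or confidence interval for the difference between the two effects

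*SAP*

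**What the plan says.** The team-swab result is the primary analysis, SAP 4.8.1 item b: "Primary Analysis: Among subjects with Day 3 qPCR results, number (%) with detectable viral shedding at Day 3". Arms are compared with a 95% CI and p-value from the normal approximation to the binomial.

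SAP 4.10 item b applies the same definition and method to the self-collected Day 3 swabs and adds: "This table can be compared to table 4.8.1a, the primary endpoint, to determine if the self-swabs would have similar treatment effects". A sub-bullet then says: "Repeat analysis in the population for the primary analysis (PEP excluding pilot study) to allow direct comparison with primary endpoint".

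The other items that bear on self-swabs do different jobs:

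- SAP 4.10 items c to f compare self and team viral loads by Bland-Altman plots, Spearman correlations and a summary of the "viral load difference between self-collected swabs and team-collected swabs on Day 0, Day 1, Day 2 and Day 3".
- SAP 4.10 item g compares arms on AUC from self-swabs alone.
- SAP 4.3.5 item b cross-tabulates detection by self- and team-collected swab, but only on Day 0, before treatment.

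The evaluation of self-collected samples is secondary objective 4 (Protocol 2.2). Protocol 3.1 and 7.3.4.5 link it to whether such samples could be used in later studies.

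**The concern.** Item b states an inferential aim, to determine whether the treatment effects are similar. The quantity that answers it is the arm difference by self-swab minus the arm difference by team swab. SAP 4.10 gives no estimate, CI or margin for that quantity. The reader gets two tables, each restricted to subjects with a Day 3 result for that swab type, and must judge similarity by eye.

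Day 3 is the only day after baseline on which Protocol Table 4 schedules both swab types. It is therefore the one point after treatment starts where the two effects can be compared within subjects. At stake is how firmly the trial can say that self-swabs preserve the treatment effect, which matters to anyone planning a later study around them.

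**Working it through.** **The plan's own figure.** The documents give no figure for this comparison. The nearest is the design sample size in Protocol 9.2.1 (42.5% vs 57.5%, 90% power, two-sided 0.05), stated as 490, or 546 after 10% missing. It reproduces:

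- Per arm without continuity correction: [1.96 × √(2 × 0.5 × 0.5) + 1.2816 × √(0.425 × 0.575 + 0.575 × 0.425)]² / 0.15² = 231.4, so 464 in total.
- With continuity correction: (231.4/4) × [1 + √(1 + 4/(231.4 × 0.15))]² = 244.6, so 245 per arm and 490 in total.
- 245/0.9 = 272.2, so 273 per arm and 546 in total.

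**Number of pairs.** The main study has 510 subjects, and 10% missing leaves 459 with a Day 3 team result. I use a round 450 pairs (225 per arm) and 50% detectable. The documents give no figure for missing self-swabs or for randomized subjects without central confirmation. With n pairs, every half-width below is multiplied by √(450/n). For example, independent 10% losses on each swab leave 510 × 0.81 = 413 pairs, a factor of 1.04.

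**Each table alone.** 1.96 × √(0.25 × 4/450) = 9.2 points.

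**Difference between effects, treated as independent.** 9.2 × √2 = 13.1 points.

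**Difference between effects, paired.** For each subject take D = self result minus team result, which is −1, 0 or 1. Its variance is approximately the discordant proportion d. The estimate is mean D in one arm minus mean D in the other, with half-width 1.96 × √(d × 4/450):

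| Discordant pairs d (assumed) | Half-width (points) | Reduction from 13.1 |
|---|---|---|
| 5% | 4.1 | 69% |
| 10% | 5.8 | 56% |
| 15% | 7.2 | 45% |
| 20% | 8.3 | 37% |
| 30% | 10.1 | 23% |

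A second calculation used 459 subjects, the design rates and a within-subject correlation phi between the two detection results. It gave 9.9, 8.1, 5.7 and 4.0 points at phi 0.4, 0.6, 0.8 and 0.9, against 12.8 if independent. The two agree, since at 50% detectable d = 0.5 × (1 − phi).

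**What side-by-side tables can show.** With 459 subjects each interval is about ±9.0 points, so two intervals overlap unless the estimates differ by about 18 points. A simulation (4,000 trials per scenario, 255 per arm, 10% missing independently on each swab, true team effect 15 points, phi 0.4 to 0.8) gave:

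| True self-swab effect | 95% CIs overlap | Paired test rejects equality |
|---|---|---|
| 7.5 points (half) | 98% to 99.9% | 31% to 69% |
| 0 points | 73% to 82% | 80% to 99.9% |

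When the true effects were identical, one table was significant and the other not in 10% to 15% of trials.

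**Can similarity be shown even with pairing?** With identical true effects and an illustrative margin of ±7.5 points, the paired 95% CI lay inside the margin in about 38% of trials at phi 0.8, and in almost none at phi 0.6 or below.

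**The case against.** The best defence is that item b is a descriptive look within an exploratory part of one secondary objective. Most of what supports that defence stands:

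- A reader might infer that the answer will turn on two p-values. The SAP sets no such rule. It shows percentages and an arm comparison with a CI as well as a p-value, on the same day, assay and method. Comparing the two point estimates is legitimate description. The overlap and significance results above show what those readings would do; the SAP does not propose them.
- A reader might infer that the two tables describe materially different subjects. The sub-bullet repeats the analysis in the primary-analysis population, so only swab-specific missing results remain. Both swabs belong to the same Day 3 visit (Protocol 6.3.6.2), so a missed visit tends to lose both. The mismatch may be small, and the completeness tables in SAP 4.8.1a and 4.10a will show much of it.
- A reader might infer that SAP 4.10 ignores pairing altogether. Items c to f use it for agreement in viral load, which is the main stated purpose. It goes unused only for the treatment effect on detection.
- The SAP never proposes to treat the two estimates as independent, so 13 points is a reference value and not a planned quantity. The gain from pairing depends on assumed discordance. The Protocol summary calls the self-collected swabs nasal and the team swabs NP, so discordance above 20% cannot be excluded.
- A paired interval without a margin still lacks a rule for calling effects similar.

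The defence does not reach the wording of item b. To determine similarity is more than to describe it, and no other item supplies the estimate.

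**Conclusion.** The point holds in a limited form. SAP 4.10b names a question about the difference between two treatment effects and plans no estimate of that difference, although the paired Day 3 data to compute it will be collected. At about 450 pairs and 50% detectable, the paired half-width is about 4 to 8 points for an assumed 5 to 20% discordance and about 10 points at 30%, against about 13 points under independence. The documents support none of the discordance values, and they give no self-swab missingness.

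The documents do not support saying that the planned comparison is worthless, that it rests on significance, or that differing subjects are its main flaw. Nor would pairing guarantee a finding of similarity. By the letters in SAP 4.8.1, the cross-reference to 4.8.1a points to the completeness item; the primary comparison is item b.

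**What to change.** Add to SAP 4.10b: in subjects of the primary-analysis population with both a self- and a team-collected Day 3 result, estimate the self-swab arm difference minus the team-swab arm difference, with a 95% CI that respects the pairing. Either a GEE with identity link and an arm-by-swab-type term or a bootstrap that resamples subjects would serve. Show both arm differences in the same subjects and the discordant counts by arm.

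Then do one of two things: state a similarity margin before unblinding, or label the comparison descriptive and replace the wording about determining similarity. Given the simulated chance of meeting a ±7.5-point margin, the descriptive label may be the realistic choice. Change the cross-reference from 4.8.1a to 4.8.1b.

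The cost is a short SAP addition and one table, with no new data. Subjects missing either swab drop out of this comparison only. The primary analysis and the sample size do not change.
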